
Non-pharmacologic strategies for addressing Agit-AD:

All participants will be provided with evidenced-based standard treatment for individuals with dementia complicated by agitation. This is an individualized approach and includes a combination of the following elements: 1) evaluation and clinical management of all medical co-morbidities that may be associated with behavioral disturbances (e.g., infection, pain, constipation, sensory problems); 2) reduction or elimination of all medications with anticholinergic effects that may adversely impact cognitive functioning and exacerbate behavioral symptoms; 3) maximization of environmental supports and non-pharmacological treatments to reduce agitation using the DICE approach (12) including but not limited to 1:1 staffing for ADL (activities of daily living) care in quiet setting and assessing environmental antecedents to behavioral agitation; 4) permission to continue and monitor all concomitant psychotropic medications; 5) incorporation of relevant elements of the psychosocial intervention used to address agitation in CitAD (33).

Exploratory biomarkers:

1) We propose to collect DNA specimens at baseline to explore the possibility that cannabinoid receptor polymorphisms may affect response to dronabinol. There has been preliminary work on the association between CB1 receptor polymorphisms and addiction (54) but none to date in AD.

While quantification of cannabinoid receptor density with neurochemical imaging could be very enlightening as to potential mechanism, it is neither practical nor ethically advisable to perform such imaging in advanced dementia and we do not propose it for this trial.

Inflammatory Markers (Cytokines):

We propose that participants will have blood drawn (approximately 42mL) to collect serum samples at Baseline and Week 3 to assay pro-inflammatory cytokines Interleukin-1 beta (IL-1 β), tumor necrosis factor-alpha (TNF- α , and Interleukin-6 (IL-6) among others. The aforementioned serum samples will be collected to examine the association of peripheral markers of inflammation with agitation and response to dronabinol. Serum will be separated within ½ hour following the draw. The sample will be stored at -80 degrees Celsius until ready to ship. The assays will be performed at an outside laboratory.

Table 2. Study Procedures by Visit

Procedure	Screening	Baseline	Week 1	Week 2	Week 3
Informed Consent Process	X				
Review of inclusion/exclusion criteria	X				
Demographics	X				

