Medical History	X				
Other Medications	X				
Randomization		X			
Study medication dispensing		X	X	X	
Coronavirus Impact Scale (CIS)		X			
Unblinding*					X *
Clinical Instruments					
Pittsburgh Agitation Scale (PAS)		X	X	X	X
Neuropsychiatric Inventory, Clinician Version (NPI-C)		X	X	X	X
Cohen-Mansfield Agitation Inventory (CMAI)		X	X	X	X
Modified Alzheimer's Disease Cooperative Study- Clinical Global Impression of Change (CGI-C)		X	X	X	X
Alzheimer's Disease Cooperative Study - Activities of Daily Living (ADCS-ADL)		X	X	X	X
Confusion Assessment Method (CAM)		X	X	X	X
Sleep Assessment (NPI-C Sleep Subscale)		X	X	X	X
Cognition					
SIB-8		X			X
Mini Mental State Exam (MMSE)		X			X
Drug Effect					
Drug Effect Questionnaire (DEQ)		X	X	X	X
Medication Side-Effects Questionnaire		X	X	X	X
Safety and AE monitoring					
Physical Exam	X				
Neurological Exam	X				
Vital Signs		X	X	X	X
General Medical Health Rating (GMHR)	X				
Adverse Event Monitoring		X	X	X	X
ECG		X			X
Blood draw (DNA, Biomarker, CBC, CMP, TSH)		X			X

*Only done after all other study procedures are complete

Protocol: Pilot trial of dronabinol adjunctive treatment of agitation in Alzheimer's disease (AD) (THC-AD)

Protocol Number: IRB00052955

Protocol Version: 6.0/2July2020

6. **Biostatistical Analysis:**

All analyses will be conducted using STATA (55) and R (56) under the supervision of the study statistician ([name]). Descriptive analyses will be conducted and measures checked for outliers and to ensure that distributional assumptions of the planned analyses are appropriate. If not, analogous non-parametric methods will be used. Analyses will be intent-to-treat. We expect minimal missing data, but if there is a significant amount of missing data, multiple imputation may be used if appropriate (57). To investigate sensitivity to missing values, those with and without missing values will be compared by background covariates. Tests will be two-sided and p-values <0.05 will be considered significant.

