Multiple test corrections will be applied as appropriate. All primary analyses will be adjusted for site as well as the variables balanced through minimization (use of antidepressants and use of antipsychotics). To account for the inclusion of multiple sites, we will include site as a covariate, with individuals being seen on an outpatient (largely remote) basis being treated as its own site. Secondarily, we will fit models with site, site x time, and site x treatment x time to determine if there are any effects of site on treatment effect over time. These analyses must be secondary as the study was not powered to detect these 3 way interactions. Importantly, no participants were stopped during their participation and all participants will have the same mode of assessment (either in-person or remote) throughout.

Aim 1: Efficacy will be assessed by fitting a longitudinal linear model with the co-primary outcomes (PAS and NPI-C Agitation/Aggression/Sum of Agitation and Aggression) and with time, treatment assignment and interaction between time and treatment. The latter term will be the coefficient of interest and will represent the mean difference in change over the 3-week period between the treated and placebo groups. Within-person correlations will be handled via the method of generalized estimating equations (58).

Aim 2: We will model risk of a severe adverse event as a function of treatment assignment using logistic regression, and counts of total adverse events using ordinal logistic regression or poisson regression as appropriate. We will also scrutinize counts of each specific type of AE as a function of treatment assignment to determine if there are specific adverse events which we should power ourselves to detect in future larger-scale trials. Special attention will be paid to new-onset delirium, seizures, and arrhythmias. Additionally we will specifically look at the effect of dronabinol on cognition using the SIB-8, and a regression model analogous to that in Aim 1. We will stratify adverse events by site and assess whether rates of particular AEs vary by site. In particular, we will assess whether outpatients differ in their rates and types of AEs (either favorably, due to being less acute, or unfavorably, due to a less controlled environment where falls might be more likely, for example).

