Secondary Analyses: We will model change in additional outcomes (e.g., CMAI, MMSE, sleep, DEQ) using models analogous to that of Aim 1. We will also look at predictors of dronabinol response, including cannabinoid receptor polymorphisms and other patient characteristics. We will also model change in IL1 β , TNF α , and IL6 as a function of treatment assignment. All secondary analyses will be conducted with site as a covariate, and additional analyses which include site x treatment and site x treatment by time will be performed.

Sample size and Power analysis

Protocol: Pilot trial of dronabinol adjunctive treatment of agitation in Alzheimer's disease (AD) (THC-AD)

Protocol Number: IRB00052955

Protocol Version: 6.0/2July2020

We observed a large effect in our observational study that used PAS as outcome. PAS is one of the co-primary outcomes and we will estimate power to detect change in PAS. There are no pilot data to estimate power to detect change in NPI-C which has not been used in prior trials of dronabinol. The PAS declined in our observational study from 9.68 (3.91) pre-treatment to 5.25 (4.17) post-treatment for a treatment effect of 1.1 and 45% reduction in PAS score.

We propose to use a more conservative estimate of 30% reduction in PAS score and calculated statistical power using the formulae of Jung and Ahn (59). A 30% reduction translates to decreasing from 9.68 PAS points to 7.26 points after 3 weeks, which means a slope of -0.81 points/week. This translates to an effect size of 0.206. It is essential to account for missing data including those from dropouts. Assuming first a missing data pattern that increases monotonically to 15% by week 3, with N= 80, a within-person correlation of 0.5 and an exchangeable correlation structure, we will have 80% power to detect a treatment effect of size 0.22, which translates to a decrease in PAS from 9.68 to 7.1 over 3 weeks; this is a 26.7% decrease. Assuming next a missing data pattern that increases monotonically to 30% by week 3, then with 80 people and a within-person correlation of 0.5 and an exchangeable correlation structure, we would have 80% power to detect a treatment effect of size 0.24, which translates to a decrease in PAS from 9.68 to 6.87 over 3 weeks; this is a 29.1% decrease. Thus, THC-AD is well-powered to detect a clinically plausible and conservatively estimate decrease in PAS which is a co-primary outcome.

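### The cytokine analysis names neither a log scale nor adjustment for the baseline level, which would cost power if the values are markedly skewed

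*Combined protocol and SAP*

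**What the plan says.** The cytokine analysis is one clause in section 6, Secondary Analyses: change in IL-1beta, TNF-alpha "and IL6 as a function of treatment assignment". The same paragraph adds "All secondary analyses will be conducted with site as a covariate", plus further models with site interactions. Section 5, Inflammatory Markers (Cytokines), plans "to collect serum samples at Baseline and Week 3", so there are two measurements per participant. Their stated purpose is "to examine the association of peripheral markers of inflammation with agitation and response to dronabinol".

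Three general rules in section 6 also bear on this:
- Measures are examined in advance: "measures checked for outliers and to ensure that distributional assumptions of the planned analyses are appropriate". If that check fails: "If not, analogous non-parametric methods will be used".
- "All primary analyses will be adjusted for site as well as the variables balanced through minimization". Those variables are antidepressant and antipsychotic use. The sentence covers primary analyses only.
- "Tests will be two-sided and p-values <0.05 will be considered significant".

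No section states the scale for the cytokines, puts the baseline level in the model, or names the non-parametric method. The sentence that borrows the Aim 1 model lists CMAI, MMSE, sleep and DEQ as examples. The cytokine sentence is separate, so it is unclear whether that model carries over.

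**The concern.** Concentrations are positive, and a drug effect on them is most naturally proportional. If they are strongly right-skewed, a difference in raw change is dominated by the few participants with high values. Subtracting the baseline also uses it less efficiently than fitting it as a covariate. Both losses can be avoided with data already collected.

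Section 1 proposes a CB2-mediated reduction in inflammation as one possible mechanism, and these assays are the plan's direct readout of it. If the scale is left open, a null result could be hard to interpret. Choosing the scale after seeing three or more markers would also invite selection. The primary efficacy and safety conclusions are not at stake.

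**Working it through.** **Plan's own figure.** There is no power statement for cytokines. The PAS power statement does reproduce: the Jung and Ahn slope formula (exchangeable correlation 0.5, linearly rising missingness) gives detectable effects of 0.216, 0.237, 0.249 and 0.274, against the stated 0.22, 0.24, 0.25 and 0.27. It says nothing about cytokines.

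**Inputs from the documents.** 80 randomised, close to 1:1; 15% or 30% missing by Week 3; two-sided 0.05. Evaluable: 80 × 0.85 = 68, or 34 per arm; 80 × 0.70 = 56, or 28 per arm.

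**Assumed.** Log-normal values; log-scale SD s from 0.3 to 1.0; log-scale correlation ρ of 0.5 or 0.7; a 30% reduction, so δ = −ln 0.7 = 0.357; no values below the assay limit.

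**Step 1: raw change against log ANCOVA, by simulation.** Log baseline = s·b and log Week 3 = s(ρb + √(1−ρ²)·e) + ln 0.7 × treatment, with b and e standard normal, 4,000 trials per setting. The methods are a t-test on raw change, a Mann-Whitney test on raw change, and regression of log Week 3 on treatment and log baseline (log ANCOVA).

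| s | ρ | Raw change | Rank test on raw change | Log ANCOVA | Loss, raw |
|---|---|---|---|---|---|
| 0.6 | 0.5 | 48% | 54% | 80% | 32 |
| 0.8 | 0.5 | 26% | 33% | 53% | 27 |
| 1.0 | 0.5 | 17% | 23% | 38% | 21 |
| 0.6 | 0.7 | 68% | 75% | 92% | 24 |
| 0.8 | 0.7 | 39% | 50% | 71% | 32 |
| 1.0 | 0.7 | 22% | 32% | 50% | 28 |

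At s = 0.3 every method exceeds 98%. With 28 per arm, s = 0.8 and ρ = 0.5, power is 21%, 27% and 45%. Under the null all methods reject in about 4 to 6% of trials.

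**Step 2: if change means log change.** With m = 34 per arm, √(2/34) = 0.2425 and power ≈ Φ(δ/SE − 1.96), where
- log change: SE = s·√(2(1−ρ))·0.2425
- log ANCOVA: SE = s·√(1−ρ²)·0.2425

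For s = 0.8 and ρ = 0.5, log change has SE = 0.8 × 1 × 0.2425 = 0.194, δ/SE = 1.84 and power Φ(−0.12) = 45%. Log ANCOVA has SE = 0.8 × 0.866 × 0.2425 = 0.168, δ/SE = 2.12 and power Φ(0.16) = 56%. The same formulas elsewhere:

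| s | ρ | Log change | Log ANCOVA | Loss |
|---|---|---|---|---|
| 0.6 | 0.5 | 69% | 81% | 12 |
| 0.8 | 0.5 | 45% | 56% | 11 |
| 1.0 | 0.5 | 31% | 40% | 9 |
| 0.6 | 0.7 | 89% | 93% | 4 |
| 0.8 | 0.7 | 66% | 73% | 7 |
| 1.0 | 0.7 | 48% | 54% | 6 |

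Simulation at s = 0.8 agrees: 44% against 56% at ρ = 0.5, and 63% against 70% at ρ = 0.7.

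**Step 3: the fallback.** A rank ANCOVA regresses the rank of Week 3 on treatment and the rank of baseline. Against log ANCOVA it has power 75% v 79% (s 0.6, ρ 0.5), 53% v 55% (0.8, 0.5), 36% v 38% (1.0, 0.5) and 69% v 72% (0.8, 0.7). The loss is 2 to 4 points.

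**Step 4: site and minimisation factors.** With four site levels (three sites, plus outpatients as their own), 68 evaluable, s = 0.8 and ρ = 0.7, power is 37% for raw change, 50% for ranks of raw change, 63% for log change and 70% for log ANCOVA. Adding antidepressant and antipsychotic use, simulated as unrelated to the cytokine, gives 68%.

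**Step 5: a smaller effect.** For a 20% reduction with site in the model and ρ = 0.7, raw change against log ANCOVA gives 19% v 34% at s = 0.8 and 12% v 24% at s = 1.0.

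**The case against.** The best reply is that the plan is silent here rather than wrong. A reader might infer that it commits to raw change with site as the only covariate. The text says neither: log change, or Week 3 adjusted for baseline, could also be described as modelling change. That stands, so the raw-change losses describe one reading of the plan, not the plan itself.

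Second, section 6 already requires a distributional check. Markedly skewed cytokines are what it should catch, so raw change is least likely to be used where it loses most. This stands in part. The replacement is unnamed, and the choice matters: a rank test on raw change leaves a loss of 15 to 26 points in the first table (for example 80 − 54 = 26 at s = 0.6, ρ = 0.5), while a rank ANCOVA leaves 2 to 4.

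Third, the figures rest on assumed skew, correlation and effect. That is true. At s = 0.5 and ρ = 0.7, with site in the model, raw change already has 84% power for a 30% reduction. With a 20% reduction or very high skew, the log model usually misses the effect too, and sample size is then the main limit.

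Fourth, a reader might take the absence of the minimisation factors as a source of lost power. No gain from adding them was shown; they would help only if they predict cytokine level.

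Finally, the cytokines come under exploratory biomarkers, with no hypothesis or power statement, and type I error is unaffected. That sets the priority.

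**Conclusion.** The gap in specification is real, and its cost depends on the data. The plan fixes neither the scale, nor the use of the baseline level, nor the fallback. For log-SD 0.6 to 1.0, correlation 0.5 to 0.7, a 30% reduction and 34 per arm, all of them assumed, raw change gives up about 21 to 32 points of power against a baseline-adjusted log model. Log change without the baseline term gives up about 4 to 12 points (7 to 12 at log-SD 0.8), so the baseline term helps on either reading of change.

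The documents do not support the stronger conclusion that following the plan would often miss a real anti-inflammatory effect. That would need the raw scale, marked skew, and a distributional check that either fails to act or leads to a weak rank test. Priority: consider.

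**What to change.** Add to section 6, Secondary Analyses: for each cytokine, log Week 3 concentration will be regressed on treatment, log baseline concentration and site, and the result reported as the ratio of geometric means (dronabinol to placebo) with 95% CI; if the distributional check fails on the log scale, the rank of Week 3 will be regressed on treatment, the rank of baseline and site.

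Because a log scale cannot take zeros, the same sentence should say how values below the assay limit are handled. Antidepressant and antipsychotic use may be added for consistency with the primary analyses, but not on grounds of power.

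The cost is wording only: both samples are already planned and no procedure changes. The one drawback is that the effect is reported as a ratio instead of a difference in concentration.

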We repeated the above power analysis assuming a sample size of 60 in the event that we do not meet our original recruitment goals. With a missing data pattern that increases monotonically to 15% by week 3, with N=60, a within-person correlation of .5 and an exchangeable correlation structure we will have 80% power to detect a treatment effect of size .25, which translates to a decrease in PAS from 9.68 to 6.75 over 3 weeks; this is a 30.3% decrease. With a missing data pattern that increases monotonically to 30% by week 3, and identical conditions otherwise, we would have 80% power to detect a treatment effect of size .27, which translates to a decrease in PAS from 9.68 to 6.51 over 3 weeks; this is a 33 % decrease.

7. Risks and Discomforts:

Study medication side effects:

Based on the list of potential side effects from clinical trials with dronabinol, items will include nausea, diarrhea, dry mouth, upset stomach, vomiting, vivid or abnormal dreams, anxiety, dizziness, fatigue, confusion, depersonalization, hallucination, paranoia, depression, rapid heart rate/palpitations, flushing in the face or body, tinnitus, speech difficulty, blurred vision, headache, sweating, runny nose, and coughing.

Potential substance abuse:

Dronabinol is a Schedule III substance indicating moderate abuse liability relative to other drugs. Given the low doses to be administered, close monitoring of participants and medication administration, and relatively short duration of exposure proposed in the present study, we believe the risk of participants misusing the study medication or becoming dependent on dronabinol to be very low. Outcomes obtained from the DEQ patient-based and informant-based questionnaires will provide outcomes relevant to examining the abuse liability of the study doses in this population (e.g. subjective ratings of pleasant drug effect) that will be valuable for future studies. We will also evaluate whether participants or families of non-responders to dronabinol request to continue medication after the trial is completed.

Protocol: Pilot trial of dronabinol adjunctive treatment of agitation in Alzheimer's disease (AD) (THC-AD)

Protocol Number: IRB00052955

Protocol Version: 6.0/2July2020

Risk of Treatment Limitations:

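### The planning effect is called a 30% PAS reduction but its figures (7.26, -0.81/week, 0.206) are those of a 25% reduction, and whether N=80 gives 80% power depends on which was meant

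*Combined protocol and SAP*

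**What the plan says.** Section 6, Sample size and Power analysis, starts from an observational series in which PAS fell from 9.68 (SD 3.91) to 5.25 (SD 4.17). It then scales the target down: "We propose to use a more conservative estimate of 30% reduction in PAS score". The conversion follows: "A 30% reduction translates to decreasing from 9.68 PAS points to 7.26 points after 3 weeks, which means a slope of -0.81 points/week". The next sentence adds: "This translates to an effect size of 0.206".

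The section then gives the effects that N=80 can detect. With missing data rising to 15% by week 3, "we will have 80% power to detect a treatment effect of size 0.22", given as a fall to 7.1 or 26.7%. With 30% missing the effect is 0.24, "which translates to a decrease in PAS from 9.68 to 6.87 over 3 weeks; this is a 29.1% decrease". It concludes: "Thus, THC-AD is well-powered to detect a clinically plausible and conservatively estimate decrease in PAS which is a co-primary outcome". For a fallback of N=60 it gives 0.25 (30.3%) and 0.27, the latter "which translates to a decrease in PAS from 9.68 to 6.51 over 3 weeks; this is a 33 % decrease"; no conclusion about adequacy is drawn for N=60.

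The Aim 1 paragraph of the same section defines the tested coefficient, the time-by-treatment interaction, as one that "will represent the mean difference in change over the 3-week period between the treated and placebo groups".

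**The concern.** The words name one planning effect and three figures describe a smaller one. The section shows this itself: it correctly labels a fall to 7.1 as 26.7%, so the smaller fall to 7.26 cannot be 30%.

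The slip matters because the detectable effects at N=80 fall between the two readings. Measured against 0.206, every effect listed as having 80% power is too large and the conclusion does not follow. Measured against 30%, both N=80 scenarios pass. This is the only power justification for N=80, since the protocol says there are no pilot data for NPI-C.

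A related wording problem affects the same sentences. The test is of a difference between arms, but each effect is translated into an absolute fall from 9.68. The two are the same only if placebo does not change. The source estimate is a pre-post change from a series that section 4 (Rationale for dosing) calls uncontrolled, and section 5 (Rationale for duration) argues from a placebo response that is largely complete by 3 weeks.

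**Working it through.** **Inputs.** From section 6: baseline PAS 9.68, SD 3.91, within-person correlation 0.5 (exchangeable), missing data rising to 15% or 30% by week 3, two-sided 0.05, N=80 or 60. From section 4: allocation close to 1:1. From section 5: visits at weeks 0, 1, 2 and 3. Assumed: linear dropout, because its shape is not given.

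**1. The target.**
- As printed: (9.68 - 7.26)/9.68 = 2.42/9.68 = 25.0%. Slope 2.42/3 = 0.807 per week. Effect size 0.807/3.91 = 0.206.
- A true 30%: 0.30 × 9.68 = 2.904, ending at 6.776. Slope 2.904/3 = 0.968 per week. Effect size 0.968/3.91 = 0.248.

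The effect size is therefore the weekly slope divided by the baseline SD. The four later conversions follow the same rule within rounding: 0.22 × 3.91 × 3 = 2.58 points, or 26.7% of 9.68, and 0.24, 0.25 and 0.27 give 29.1%, 30.3% and 32.7%. Only the planning target breaks it.

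**2. Reproducing the detectable effects.** For a GEE comparison of slopes,

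SE² = s² / (μ₀² σ⁴ · r(1 - r) · N), with r = 0.5.

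Here pⱼ is the proportion observed at time tⱼ, μ₀ = Σpⱼ, τ = Σpⱼtⱼ/μ₀, σ² = Σpⱼ(tⱼ - τ)²/μ₀, and s² = ΣΣ pⱼₖρⱼₖ(tⱼ - τ)(tₖ - τ). Under monotone dropout pⱼₖ is the smaller of pⱼ and pₖ.

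- 15% missing, p = (1, 0.95, 0.90, 0.85): μ₀ = 3.70, σ² = 1.245, s² = 2.515, so N·SE² = 0.474.
- 30% missing, p = (1, 0.90, 0.80, 0.70): μ₀ = 3.40, σ² = 1.228, s² = 2.502, so N·SE² = 0.574.

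The effect with 80% power is (1.960 + 0.842) × SE.

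| N | Missing | SE | Computed | Printed |
|---|---|---|---|---|
| 80 | 15% | 0.0770 | 0.216 | 0.22 |
| 80 | 30% | 0.0847 | 0.237 | 0.24 |
| 60 | 15% | 0.0889 | 0.249 | 0.25 |
| 60 | 30% | 0.0978 | 0.274 | 0.27 |

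All four agree to two decimals. A one-sided test does not reproduce them (0.191 and 0.211 at N=80).

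**3. Power for each target.** Power = Φ(effect/SE - 1.96). For example, 0.206/0.0770 - 1.96 = 0.715, giving 76%.

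| Target | N=80, 15% / 30% missing | N=60, 15% / 30% missing | N for 80% power, 15% / 30% missing |
|---|---|---|---|
| 0.206 (25%) | 76% / 68% | 64% / 56% | 88 / 106 |
| 0.248 (30%) | 90% / 83% | just under 80% / 72% | 61 / 74 |

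The last column is (2.802/effect)² × N·SE², with the unrounded effects 0.2063 and 0.2476. For example, (2.802/0.2063)² × 0.474 = 87.4, so 88.

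Scaling from the printed 0.22 and 0.24 instead gives much the same power at N=80: 75% and 67% for the 25% target, 88% and 82% for the 30% target.

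**4. Dependence on missing data.** With none missing the SE at N=80 is 0.0707, and 0.206 has 83% power. Power is 81% at 5% missing by week 3, just under 80% at 7.5%, and 79% at 10%.

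**5. Placebo change.** If 30% is the fall in the drug arm itself, the printed percentages leave room at N=80 for a placebo fall of 30 - 26.7 = 3.3 percentage points (2.904 - 2.58 = 0.32 PAS points) with 15% missing. With 30% missing they leave 30 - 29.1 = 0.9 (2.904 - 2.81 = 0.09 points). If 30% is already net of placebo, no margin is used up.

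**The case against.** The strongest reply is that 30% was plainly meant. The protocol names 30% twice and never prints 25%. The detectable falls of 26.7% and 29.1% support the conclusion only against 30%, and 0.206 does not enter any of the four detectable-effect calculations. On this view three converted figures are a slip and the conclusion for N=80 is intact. That may well be the likelier history. It does not settle the matter, because the end score, slope and effect size agree with each other at 25%, and no other part of the document says which is right.

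Second, the shortfall under 0.206 depends on missing data, which section 6 expects to be minimal; with none missing, N=80 reaches 83%. This is correct. But the power section itself calls allowance for missing data essential and reports only 15% and 30%, and under both of these 0.206 falls short.

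Third, the detectable effects are already between-arm quantities, since the cited method compares slopes, so only the translation into end scores is loose. This stands. The placebo margins apply only if 30% is the fall in the drug arm, and the protocol gives no size for a placebo fall. The request on this point is for clearer wording.

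**Conclusion.** The concern holds. The stated planning effect contradicts itself, and as printed the conclusion does not follow from 0.206, which is smaller than all four effects listed at 80% power.

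- If 25% (0.206) is the target, N=80 has about 76% or 68% power with 15% or 30% missing.
- If 30% (0.248) is the target, N=80 has about 90% or 83%, and the conclusion stands for N=80, provided the 30% is a difference from placebo or placebo does not change.

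The 25% finding is plain arithmetic and needs no model. The powers rest on linear dropout, 1:1 allocation, correlation 0.5 and an unadjusted two-sided 0.05; any multiplicity correction across the co-primary outcomes would lower them. The point should be fixed, but it is not fatal, because one reading preserves the conclusion and the design and test are unaffected.

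**What to change.** Choose one target and make its four expressions agree:

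- **25% reduction:** 9.68 to 7.26, -0.81 per week, effect size 0.206. State power of about 76% and 68% at N=80 and 64% and 56% at N=60 (15% and 30% missing); or
- **30% reduction:** 9.68 to 6.78, -0.97 per week, effect size 0.248. State power of about 90% and 83% at N=80, and just under 80% and 72% at N=60.

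Say that the target and all detectable effects are differences beyond placebo. For example, 0.22 is 0.22 × 3.91 = 0.86 points per week, or about 2.6 PAS points more improvement than placebo at week 3. In the same way 0.24, 0.25 and 0.27 are about 2.8, 2.9 and 3.2 points.

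Limit the claim of good power to scenarios that reach 80%, and state the alpha used. Label any power quoted under an assumed placebo fall as illustrative.

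The cost is wording and, under the 25% target, a less favourable stated power. More participants (88 or 106 instead of 80) are needed only if the sponsor chooses 0.206 and still wants 80% power with 15% or 30% missing.
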